**Sponsor/Quotient Sciences Confidential**

---

**14.5.10 Abnormal Laboratory Findings**

In cases where laboratory findings are outside the normal range and the investigator believes that the results may be of clinical significance, repeat sampling may be requested as clinically indicated. If the abnormal finding is clinically significant, appropriate actions will be taken e.g. the participant will not be entered into the study or the participant may be withdrawn from the study. The participant will be referred to their general practitioner or other appropriate provider for further care if necessary. The same will apply if the results of the HBsAg, HCV Ab or HIV test are positive and in addition the investigator will ensure that adequate counselling is available if requested.

Abnormal results at any unscheduled follow-up assessments will also require repeat testing if the investigator believes the results may be of clinical significance.

Any clinically significant abnormality, including changes from baseline, must be reported as an AE.

Additional blood and/or urine samples may be taken for safety tests. Furthermore, additional assays outside those specified in the protocol may be performed for safety reasons as requested by the investigator or sub-investigator.

**14.6 Vital Signs Measurements**

Blood pressure and heart rate will be measured by an automated recorder after the participant has been in a supine position for a minimum of 5 min and oral temperature and respiratory rate will be measured according to the time schedules presented in [Appendix 2](#)[Appendix 5](#), [Appendix 6](#) and [Appendix 7](#).

Blood pressure and heart rate orthostatic measurements will also be taken according to the time schedules presented in [Appendix 5](#), [Appendix 6](#) and [Appendix 7](#). Two measurements will be recorded; 1 supine and 1 standing. The first supine measurement will be performed after the participant has rested in a supine position for at least 5 min. The second blood pressure and heart rate measurements will be performed after the participant has been standing for at least 3 min but no more than 5 min. Orthostatic hypotension will be defined as either:

- A decrease of SBP  $\geq$  20 mmHg after 3 min standing, or
- A decrease of DBP  $\geq$  10 mmHg after 3min standing

The acceptable deviations from the nominal vital signs measurement time points are:

- Day 1 in all parts and Day 8 in Part 2: The pre-dose vital signs measurements will be taken  $\leq$  2 h before dosing
- On Days 2 and 3 (Part 3 only): the pre-dose vital signs measurements will be taken  $\leq$  1 h before dosing.
- Post-dose vital signs measurements will be taken  $\pm$  15 min from the nominal post-dose time point.
- For return visits, vital signs measurements will be taken  $\pm$  2 h from the nominal return visit time point.
- End of study visit vital signs measurements will be taken  $\pm$  1 day from the nominal time point.

**Sponsor/Quotient Sciences Confidential**

---

If a participant shows an abnormal assessment at any stage, repeat measurements may be made and the abnormality followed to resolution if required. Additional measurements may be taken as deemed necessary by the investigator or sub-investigator.

Any clinically significant abnormality, including changes from baseline, must be reported as an AE.

#### **14.7 ECG Measurements**

Single 12-lead ECGs will be measured after the participant has been in the supine position for a minimum of 5 min according to the time schedules presented in [Appendix 5](#), [Appendix 6](#) and [Appendix 7](#).

TriPLICATE 12-lead ECG measurements will be performed at least 2 min and no longer than 4 min apart after the participant has been in the supine position with no external stimuli (e.g. music or television) for 15 min prior to the nominal time point where a triplicate ECG is scheduled ([Appendix 5](#), [Appendix 6](#) and [Appendix 7](#)). No other procedures should be performed within the 15 min resting period.

The acceptable deviations from the nominal ECG measurement time points are:

- Post-dose triplicate ECG resting periods will be ended within  $\pm$  15 min of the nominal time point
- Day 1 only: The pre-dose ECG measurements will be taken  $\leq$  2 h before dosing
- On Days 2 and 3 (Part 3 only): the pre-dose ECG measurements will be taken  $\leq$  1 h before dosing.
- Post-dose ECG measurements will be taken  $\pm$  15 min from the nominal post-dose time point.
- For return visits, ECG measurements will be taken  $\pm$  2 h from the nominal return visit time point.
- End of study ECG measurements will be taken  $\pm$  1 day from the nominal time point.

The ECGs will be collected electronically and over-read by cardiologists at Banook. The Banook over-read will be used for cardiac safety evaluations during SAC data review.

For safety assessments, a mean value for the triplicate ECGs will be reviewed.

If a participant shows an abnormal assessment at any stage, repeat measurements may be made and the abnormality followed to resolution if required. Additional measurements may be taken as deemed necessary by the investigator or sub-investigator.

Any clinically significant abnormality, including changes from baseline, will be reported as an AE.

#### **14.8 Holter (continuous ECG) Monitoring**

All ECGs will be collected electronically using a Mortara H12+ Holter Recorder, and analysed by Banook. Specific procedures for ECG Holter recording and extractions will be provided to the investigator by Banook.

**Sponsor/Quotient Sciences Confidential**

---

According to the time schedules presented in [Appendix 5](#), [Appendix 6](#) and [Appendix 7](#), continuous Holter monitoring will commence at least 1.5 h prior to dosing until at least 24 h post-dose. Participants will be required to rest in the supine position with no external stimuli (e.g. music or television) for 15 min prior to the nominal time point where an ECG extraction is scheduled. This extraction will be taken by the third party Holter provider at the planned time and therefore no other procedures should be performed within the resting period.

Where one period of ECG rest runs into the rest period for the next ECG extraction, the minimum resting period before ECG extraction does not need to be started again except in cases where the rest is disturbed (e.g. participants has to get up for a comfort break after the preceding rest period).

Participants may move more freely outside of the primary ECG rest periods. Comfort breaks for hygienic purposes will be allowed each morning well in advance of the required supine/ECG extraction points.

Where any scheduled rest times are missed, where there is less than a 10 min rest period or where the final 5 min of a rest period is interrupted (for example, by participant movement or loss of leads) a protocol deviation will be recorded and the Holter provider informed.

Loss of leads or interruption of the recording outside of the scheduled rest times will not be considered a protocol deviation but should be recorded in the source.

The acceptable deviations for ECG rest periods from the nominal time point are:

- Pre-dose and post-dose ECG resting periods will be ended within  $\pm$  15 min of the nominal time point

See [Section 10.3.2](#) for details on timing of Holter rest period/extractions in relation to other procedures and [Appendix 7](#) for rest period/extraction time points.

The ECGs will be collected electronically and over-read by cardiologists at Banook. The Banook over-read will be used for cardiac safety evaluations during SAC data review.

#### **14.9 Telemetry (Continuous ECG)**

On Day 1 of Parts 1 and 2, telemetry (continuous ECG monitoring) will commence at least 30 min before dosing until at least 12 h post-dose. As this monitoring is for safety purposes alone no data will be recorded in the source, except the start and stop time. If cardiac monitoring shows a potentially significant abnormality, a clinical assessment of the participant including a 12-lead ECG will be performed and treatment given, if appropriate.

#### **14.10 Body Weight, Height and BMI**

The participant's body weight and height will be measured and their BMI will be calculated according to the time schedules presented in [Appendix 2](#), [Appendix 3](#) and [Appendix 4](#).

#### **14.11 Physical Examination**

Participants will undergo a physical examination according to the time schedules presented in [Appendix 2](#), [Appendix 3](#) and [Appendix 4](#).

---

**Sponsor/Quotient Sciences Confidential**

---

In the targeted (symptom driven) physical examination, a physician will assess the participant; if the participant reports feeling unwell or has ongoing AEs, then the physician will examine the appropriate body system(s) if required.

**14.12 Beck Depression Inventory (BDI-II) Questionnaire**

Each participant will undergo a BDI-II questionnaire [7], according to the time schedules presented in [Appendix 2](#), [Appendix 3](#) and [Appendix 4](#). A participant will be excluded from the trial if they have a score of 20 or more on the BDI-II, and/or a response of 1, 2 or 3 for item 9 of this inventory (related to suicidal ideation).

Individuals with a BDI-II score of 17-19 may be enrolled, at the discretion of the investigator, if they do not have a medical history of psychiatric conditions and their mental state is not considered to pose additional risk to the health of the individual or to the execution of the trial and interpretation of the data.

**14.13 Additional Safety Procedures**

Additional non-invasive procedures that are already specified in the protocol may be performed, if it is believed that an important effect of the IMP(s) is occurring or may occur at a time when no measurements are scheduled, or if extra procedures are needed in the interests of safety.

Additional blood samples for safety assessments may be taken if required by the investigator or sub-investigator at any point.

**15 Statistics and Data Analysis****15.1 Sample Size Justification**

For Parts 1 and 3, the primary objective is an initial assessment of safety and each treatment group is therefore limited to 6 participants receiving active IMP. Administration of MMV367 to 6 participants at each dose level provides a 47%, 62%, 74%, or 82% probability of observing at least 1 occurrence of any AE, with a true incidence rate for a given dose group of 10%, 15%, 20%, or 25%, respectively.

Furthermore, it is assumed that pooling the data for the 2 participants who receive placebo in each cohort will provide an adequately sized control group to assess a possible drug effect on safety laboratory tests, vitals and ECG parameters.

Part 2 is a pilot evaluation designed to determine whether MMV367 PK is impacted by high-fat food. Historically, 8 participants have proven sufficient to characterise the preliminary effects of food on safety and PK of a new chemical entity in healthy participants. Therefore, a sample size of 8 is considered adequate at this stage of drug development.

**Sponsor/Quotient Sciences Confidential****15.2 Data Management**

Data management will be performed by Quotient.

Study data will be managed using a validated electronic case report form (eCRF) database system and will be subjected to data consistency and validation checks. Data queries will be raised within the study eCRF database by data management staff and resolved with the assistance of clinical staff.

AEs, medical histories and medications will be coded using the Medical Dictionary for Regulatory Activities (version to be specified in the Data Management Plan [DMP]) and the World Health Organization Drug Dictionary Global Drug Reference (version to be specified in the DPM), respectively. An independent coding review will also be performed within the Data Sciences department.

Clinical chemistry, haematology and coagulation data (and other safety laboratory data) will be collected by a central laboratory (The Doctors Laboratory) and stored electronically in their clinical pathology system. The data will be transferred electronically to Quotient and all demographic details and sample dates will be cross-referenced with the corresponding data on the study database. All queries will be resolved with the assistance of laboratory staff, or if necessary, clinical staff.

The database will be closed after all queries have been resolved. The database will be locked when all criteria listed in the DMP are met.

Further details are addressed in the DMP.

**15.3 Pharmacokinetic Data Analysis**

The plasma concentration data for MMV367 provided by Swiss BioQuant will be analysed by Quotient, using Phoenix WinNonlin v8.3 or a more recent version (Certara USA, Inc., USA).

PK analysis of the concentration time data obtained will be performed using appropriate non-compartmental techniques to obtain estimates of the PK parameters presented in [Table 7](#) and [Table 8](#), where possible and appropriate.

**Table 7 Plasma Pharmacokinetic Parameters: Part 1 and 2**

Parameter	Definition
Tmax	Time of maximum observed concentration
Cmax	Maximum observed concentration
AUC(0-24)	Area under the curve from time 0 to 24 h post-dose
AUC(0-48)	Area under the curve from time 0 to 48 h post-dose
AUC(0-last)	Area under the curve from time 0 to the time of last measurable concentration
AUC(0-inf)	Area under the curve from time 0 extrapolated to infinity
T1/2	Terminal elimination half-life
CL/F	Total body clearance calculated after a single extravascular administration where F (fraction of dose bioavailable) is unknown
Vz/F	Apparent volume of distribution based on the terminal phase calculated using AUC(0-inf) after a single extravascular administration where F (fraction of dose bioavailable) is unknown
Frel Cmax	Relative bioavailability based on Cmax (Part 2 fed dosing only)

**Sponsor/Quotient Sciences Confidential**

Parameter	Definition
Frel AUC(0-last)	Relative bioavailability based on AUC(0-last) (Part 2 fed dosing only)
Frel AUC(0-inf)	Relative bioavailability based on AUC(0-inf) (Part 2 fed dosing only)

**Table 8 Plasma Pharmacokinetic Parameters: Part 3**

Parameter	Definition
Tmax	Time of maximum observed concentration
Cmax	Maximum observed concentration
AUC(0-tau)	Area under the curve for the defined interval between doses (tau)
T1/2	Terminal elimination half-life (Day 3 only)
CL/Ftau	Total body clearance calculated using AUC(0-tau) after repeated extravascular administration where F (fraction of dose bioavailable) is unknown (Day 3 only)
Vz/Ftau	Apparent volume of distribution based on the terminal phase calculated using AUC(0-tau) after repeated extravascular administration where F (fraction of dose bioavailable) is unknown (Day 3 only)
AR Cmax	Accumulation ratio based on Cmax repeated dose/Cmax single dose (Day 3 only)
AR AUC	Accumulation ratio based on AUC(0 tau) repeated dose/AUC(0 tau) single dose (Day 3 only)

Analysis of drug related QT/QTc interval changes relative to plasma PK concentrations will be conducted. This analysis will be performed on the analysis set for intensive cardiac assessment. Concentration/QTc modelling may be performed after completion of the CSR and will be reported separately.

In Part 1 Cohorts 1C and 1D, provided a future bioanalytical method is available, urine concentration data for MMV367, provided by Swiss BioQuant, will be analysed by Quotient and reported in an addendum to the CSR or in a separate report. Estimates of the parameters presented in [Table 9](#) in urine will be obtained where possible and appropriate.

**Table 9 Urine Pharmacokinetic Parameters: Part 1, Cohorts 1C and 1D only**

Parameter	Definition
CLr	Renal clearance calculated using plasma AUC
Ae	Amount excreted
CumAe	Cumulative amount excreted
%Ae	Percentage of dose excreted
Cum%Ae	Cumulative percentage of dose excreted

Interim PK parameter estimations will be provided as described in [Section 8.2](#).

Further details of the PK data analysis will be included in the reporting and analysis plan (RAP).

**Sponsor/Quotient Sciences Confidential**

---

**15.4 Metabolite Profiling and Identification Assessment**

Metabolite profiling of MMV367 in plasma and urine will be performed using existing PK samples (pooled residual samples) collected in Part 1. Potential metabolites will be identified using liquid chromatography-mass spectrometry analysis. If results suggest that a major metabolite is present in plasma (e.g. greater than 10% of circulating MMV367 in plasma based on peak AUCs), metabolite quantification and PK analysis in plasma will be performed provided a future bioanalytical method is available. These results may be reported in an addendum to the CSR or in a separate report.

**15.5 Statistical Data Analysis**

Statistical analysis and production of summary tables, figures and listings for this study will be performed by Quotient using the statistical package SAS (v9.4 or more recent version).

In general terms, categorical data (including treatment-emergent AEs) will be presented using counts and percentages, while continuous variables will be presented using the mean, median, standard deviation, minimum and maximum. Additional statistics will be provided for PK-related data including coefficient of variation (CV%), geometric mean and geometric CV%.

Descriptive summaries for all safety data (AEs, vital signs, ECGs and safety laboratory assessments) by regimen will be provided (including changes from baseline as required).

Descriptive summaries for all PK data by regimen will be provided.

All safety and PK data will be listed.

**Assessment of Dose Proportionality**

For Part 1, dose proportionality will be assessed using a power model approach using log-transformed Cmax, AUC(0-last) and AUC(0-inf) values, including data from up to 5 different dose levels, i.e., general linear model including log dose as a fixed effect and log PK parameter as the dependent variable. The estimate obtained for  $\beta$  together with its 90% confidence interval (CI) will be presented along with the number of participants and the geometric means. The resulting estimate slope ( $\beta$ ) and 90% CI is a measure of dose proportionality; the relationship is considered dose proportional when  $\beta = 1$ .

**Assessment of Taste Questionnaire Data**

In Part 1, formal statistical analysis will be performed on the scores of each taste attribute and overall acceptability, in the comparison of each dose level of MMV367 to the pooled placebos, using non-parametric methods. Hodges-Lehmann estimation methods will be used to estimate the median difference between each dose level and the pooled placebos. The associated 95% CI will be calculated for the estimate. The p-value will be calculated from the Wilcoxon Rank Sum Test (Mann-Whitney-Wilcoxon Test) for the test of the null hypothesis that the difference between the medians of each dose level and the pooled placebos is equal to zero, with the alternative hypothesis being that the difference is not equal to zero.

The number of participants and the median score for each treatment will be presented together with the Hodges-Lehmann estimate of the median difference and associated 90% CI. In addition, the p-value from the Wilcoxon Rank Sum Test will also be presented.

**Sponsor/Quotient Sciences Confidential**

---

**Assessment of Food Effect**

In addition, for Part 2, formal statistical analysis will be performed, at a minimum, on the following PK parameters: Cmax, AUC(0-last) and AUC(0-inf), to assess for the effects of food. The PK parameters will undergo a natural logarithmic transformation and will be analysed using a mixed effect model with terms for fed/fasted status and period fitted as fixed effects and participant fitted as a random effect. The adjusted mean difference between the fed and fasted states, and the associated 90% CI obtained from the model are back transformed on the log scale to obtain the adjusted geometric mean ratio and 90% CI of the ratio. These will be presented together with the p-value from the fed/fasted comparison.

A categorical analysis of QTcF data will be reported ([Table 10](#)).

**Table 10 QTcF Categorical Analysis**

Absolute QTcF prolongation	

• QTcF >450 msec

• QTcF >480 msec

• QTcF >500 msec

Change from baseline in QTcF	

• QTcF increases from baseline >30 msec

• QTcF increases from baseline >60 msec

Populations and analysis sets will be determined for safety, PK and taste data after database lock using the criteria defined in the RAP; the RAP will be signed off prior to database lock.

The safety population and safety analysis set will be defined after database lock but prior to study unblinding; all other populations and analysis sets will be defined after database lock and unblinding when the relevant data are available.

Further details relating to the statistical analysis will be included in the RAP including the following:

- Criteria to be used to define each of the population and analysis sets
- Additional detail covering the analyses and/or description of primary and secondary analyses and safety data
- Handling of missing data, unused or spurious data
- Handling of data from withdrawn participants
- Unblinding procedures and maintaining the blind

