**Sponsor/Quotient Sciences Confidential**

---

case of a medical emergency, or if warranted during scheduled safety reviews. The medical monitor must be contacted within 24 h following disclosure of study drug assignment.

Details of any disclosure of the randomisation schedule will be documented and retained in the ISF. The sponsor will be notified if the study blind is broken.

The study blind will be broken after the study database has been locked and the safety population has been defined. Any subsequent request for issue of the randomisation schedule prior to unblinding must be made using a randomisation disclosure form.

Part 2 of the study is open-label and therefore blinding is not required.

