## **6.2 Taste Population and Taste Analysis Set**

The taste population will include all subjects who have received at least one regimen (i.e., active dose or placebo), in Part 1, and held it in their mouth for approximately 10 to 15 seconds. Participants will have also completed the taste questionnaire for a regimen and have no relevant protocol deviations for any taste test or AEs which confound the taste assessment.

The taste population will be determined by Quotient with approval from MMV after database lock and will be used for the taste tables and to determine the participants to be included in the taste analysis set.

---

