**Table 14 Reporting Conventions for Summary Statistics and Statistical Analysis**

Data Type	Statistic	Number of decimal places for reporting (i)
Frequency	Counts (n)	None
	Percentages (%)	1 decimal place
Summary statistic	n	None
	Mean	i + 1 decimal places
	Median	i + 1 decimal places
	SD	i + 1 decimal places
	Min	i decimal places
	Max	i decimal places
	CV%	1 decimal place
	Geometric n	None
	Geometric Mean	i + 1 decimal places
	Geometric SD	i + 1 decimal places
Statistical analysis	Geometric CV%	1 decimal place
	Ratios (%)	2 decimal places
	Confidence intervals (%)	2 decimal places
	p-values	if <0.001: presented as <0.001
		if ≥0.001 and <0.099: presented to 3 decimal places
		all other p-values will be presented to 2 decimal places

i refers to the number of decimal places reported in the eCRF or other appropriate source data for the original data. Where bioanalytical or PK data are received rounded in significant figures rather than decimal places, summary statistics will be supplied to the same precision.

Details of how the individual PK parameters will be presented are detailed in [Section 9.1.1](#). Where data requires rounding, values ending with 1 to 4 will be rounded down and values ending with 5 to 9 will be rounded up.

All data listings will be based on all enrolled subjects (as defined in [Section 3.2.3](#)). Details of age and sex will be included on all data listings.

For the assessment of food effect in Part 2, statistical tests relating to PK parameters will be 2-sided and will be performed using a 10% significance level, leading to 90% (2-sided) confidence intervals (CIs).

If any baseline measurements are found to be missing then consideration will be given to imputation using the preceding time point (e.g., screening, admission, if applicable). Unscheduled assessment may be used if appropriate. Details of any such imputations will be documented as part of the safety analysis set.

There will be no other imputations for the safety data with regard to missing values or study discontinuation (i.e., subjects who do not complete the study). Imputation for PK parameter estimation using WinNonlin is described in [Section 9.1.2](#). Imputations for reporting PK data are described in [Section 9.1.3](#).

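### The exploratory taste comparison lets undefined exclusion criteria be applied with treatment known, sets no onset limit on excluding adverse events, and gives two confidence levels for one estimate

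*Protocol*

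**What the plan says.** **The analysis.** Protocol 15.5 (Assessment of Taste Questionnaire Data) plans a formal analysis of seven taste attributes and overall acceptability, "in the comparison of each dose level of MMV367 to the pooled placebos, using non-parametric methods". The estimate is the Hodges-Lehmann median difference. The test is a two-sided Wilcoxon rank sum test, "with the alternative hypothesis being that the difference is not equal to zero".

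**Timing.** Protocol 15.5, below Table 10, names safety, PK and taste populations. Their criteria are to be in the reporting and analysis plan (here, the SAP), signed before database lock. The safety population is defined after lock but before unblinding; "all other populations and analysis sets will be defined after database lock and unblinding when the relevant data are available". Protocol 8.8.2 adds: "The study blind will be broken after the study database has been locked and the safety population has been defined". SAP 6.1 confirms the safety population before unblinding in Parts 1 and 3. SAP 6.2 places the taste population after database lock, by the contract research organisation with sponsor approval, and does not mention unblinding.

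**Criteria.** Under SAP 6.2 participants must have held the product in the mouth, completed the questionnaire, and "have no relevant protocol deviations for any taste test or AEs which confound the taste assessment". Neither a relevant deviation nor a confounding event is defined, and no onset time is given.

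**Confidence level.** Protocol 15.5 first says "The associated 95% CI will be calculated for the estimate". Its next paragraph presents the "Hodges-Lehmann estimate of the median difference and associated 90% CI". The synopsis repeats both. SAP mock Table 14.6.1.3 shows 90%.

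**The concern.** PK populations have a reason to wait: SAP 6.3 confirms them once all PK parameters have been derived. Taste has no such reason. The questionnaire is filled in straight after swallowing and within 10 minutes of dosing (Protocol 8.1.1 and 13.3), needs no bioanalysis, and goes into the study database. Nothing is gained by waiting until treatment is known.

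The adverse-event rule adds to this. Protocol 6.4.1 lists gastrointestinal toxicity, with nausea and vomiting, first among the potential drug risks. An event close enough to tasting to be called confounding could be the participant's reaction to the product, which is what the questionnaire sets out to measure. Excluding that person would remove a score that is probably low. With six active participants per dose, one exclusion is 1/6, or 17%, of the group.

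The two confidence levels matter because no significance level is given for taste. The only one in the SAP (10%, section 14.1) is tied to the Part 2 food-effect tests, so nothing else in the documents settles which interval is meant.

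**Working it through.** **Plan's own figures.** Neither document gives a sample size, power or significance level for taste. The only design figures are for six active participants per dose (Protocol 15.1): the chance of at least one adverse event is 1 − (1 − p)^6. At p = 10%, 15%, 20% and 25% this gives 46.9%, 62.3%, 73.8% and 82.2%, matching the stated 47%, 62%, 74% and 82%.

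**Group sizes.** Each Part 1 cohort has 6 active and 2 placebo participants (Protocol 8.1.1). Five cohorts give 5 × 2 = 10 pooled placebo. Without optional Cohort 1E there are 4 × 2 = 8.

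**Can exclusions be decided with treatment known?** Set side by side:

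| Population | Protocol 15.5 | SAP |
|---|---|---|
| Safety | after lock, before unblinding | before unblinding in Parts 1 and 3 (6.1) |
| Taste | after lock and unblinding | after lock; silent on unblinding (6.2) |

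The protocol puts taste after unblinding and the SAP does not bring it forward. The categories are fixed in advance, but deciding who falls into them is not.

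**Effect of one exclusion (illustration).** Scores are drawn from a normal distribution with mean 5 and SD 2, rounded and clipped to 1–9, with no true difference, 6 active against 10 placebo. Mean and SD are assumptions; the documents give neither. Mean Hodges-Lehmann estimate over 20,000 simulated comparisons:

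| Participants removed | Mean estimate |
|---|---|
| None | about 0.0 |
| Lowest active score | about +0.47 |
| One random active participant | about 0.0 |
| Lowest score in each arm | about +0.17 |

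With 8 placebo participants, dropping the lowest active score gives about +0.46. With 10 placebo participants, that shift runs from about +0.24 at SD 1 to about +0.55 at SD 2.5. The sampling SD of the estimate at SD 2 is about 1.1 points, so the worst-case shift is less than half of it.

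**Two confidence levels.** With 6 against 10 there are 6 × 10 = 60 pairwise differences and 8,008 equally likely rank arrangements under the null (no ties assumed).

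- Nominal 95%: the largest k with P(U ≤ k) ≤ 0.025 is 11, with 168 arrangements. The interval runs from the 12th to the 49th ordered difference. Coverage is 1 − 2 × 168/8008 = 95.8%, so zero is excluded in 4.2% of null comparisons.
- Nominal 90%: the largest k with P(U ≤ k) ≤ 0.05 is 14, with 374 arrangements. The interval runs from the 15th to the 46th. Coverage is 1 − 2 × 374/8008 = 90.7%, so zero is excluded in 9.3%.

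With 8 placebo participants the coverages are 95.7% and 91.9%. The large-sample width ratio is 1.960/1.645 = 1.19. Scores on a 9-point scale will be tied, so the exact percentages are a guide only.

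**The case against.** **The criteria are fixed in advance.** This stands. A reader might infer that the taste population is chosen freely after unblinding. Protocol 15.5 rules that out by requiring the criteria in a plan signed before lock. What remains open is how two undefined terms are applied to individuals.

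**A confounding event need not be a drug effect.** This also stands. Protocol 14.1 counts events before dosing. Exclusion criterion 9 bars conditions affecting smell or taste, such as a cold or mouth ulcer, but Protocol 9.3 does not list it among the criteria re-assessed at admission. A cold that starts between screening and Day 1 would rightly be covered. This supports keeping an adverse-event rule, but not one without an onset limit.

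**The +0.5 shift is constructed.** Agreed: it always removes the lowest active score and never a placebo score. It shows what the rule allows. It is no forecast, and the sign of any actual bias is not established.

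**Exclusions would be visible.** SAP 7.3 and 7.4 tabulate reasons for exclusion by arm, and SAP 10.2 lists all taste data, so a reader could repeat the analysis with everyone included. That limits the harm, but does not replace deciding blind.

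**The reported interval is clear enough.** The protocol's presentation sentence and the SAP mock table both use 90%, which makes 90% the natural choice. The 95% statement still stands in both the protocol body and the synopsis.

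**Conclusion.** The point holds, at modest weight. The documents allow judgemental exclusions from the taste analysis with treatment known, the adverse-event exclusion can catch a reaction to the product, and the protocol contradicts itself on the confidence level. The first two are a route to bias, not demonstrated bias. Their size, about +0.5 points for one worst-case exclusion, rests on the assumed SD of 2, no true difference, and the lowest active score being the one removed. The contradiction needs no assumption.

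Two stronger readings should be avoided. A reader might infer that a biased taste result would steer formulation choice; no passage gives it that use, and the dose-decision rules in Protocol 8.2.2 rest on safety, tolerability and PK. A reader might also call this the trial's only formal active-versus-placebo test. That is true of the analyses described in these two documents, but the ECG exposure-response work is reported separately under a plan not included here.

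Taste is an exploratory objective. Primary safety and secondary PK conclusions are unaffected.

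**What to change.** 1. Protocol 15.5 and SAP 6.2: define the taste population and analysis set before unblinding, at the same review as the safety population.
2. SAP 6.2: limit the adverse-event exclusion to events with onset before tasting, and say what makes a deviation relevant.
3. Protocol 15.5, synopsis and SAP: state one confidence level, 90%, as in SAP mock Table 14.6.1.3.

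As a clerical matter, add the Wilcoxon and Hodges-Lehmann method to SAP section 10, which has no text on it, and list Table 14.6.1.3 in the SAP index of tables, which omits it.

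The cost is one more item in an already planned blinded review, plus minor wording changes to both documents. Because Protocol 15.5 and the synopsis change, this needs a protocol amendment as well as a SAP edit. No extra data, participants or visits are needed.
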